13.1.2 Method of Analysis for Non-Repeated Continuous Endpoints

Treatment group comparisons on endpoints that are continuous variables not assessed repeatedly will be done using GLM with change from baseline as the dependent variable, treatment group as an independent variable, and baseline observation as a covariate (if applicable). Model-based LS means will be reported for each treatment group, along with CIs and p-values for treatment group comparisons.

Model assumptions will be evaluated using diagnostic tools such as Q-Q and scatter plots of residuals, and sensitivity analyses using alternative methods (e.g., rank-based) will be considered if there appear to be substantial deviations from model assumptions. Outlier assessment will be done using visual inspection (e.g., box-and-whisker plots) and potential outliers will be investigated for data entry accuracy and biological consistency. If unexplainable outliers are present, a sensitivity analysis may be done excluding the outliers to assess their effect on the analysis conclusion.

A random effects linear model will be used to assess the impact of site, as a random effect, on treatment effect estimates. If the effect is appreciable, a random effects model will be used in place of GLM.

13.1.3 Method of Analysis for Repeated Binary Endpoints

Treatment group comparisons on binary endpoints assessed repeatedly will be done using GEE with nominal visit (time) and treatment group as main effects, treatment-by-time as an interaction term, an appropriate baseline value as a covariate (if applicable); and correlated errors within subject.

Confidential Page 23 of 33

The working correlation structure will initially be specified as unstructured but other structures may be explored by examining the covariance matrix and using goodness-of-fit measures (e.g., Quasilikelihood under the Independence model Criterion). P-values for treatment group comparisons will be reported for each nominal visit. A p-value for treatment group comparison over all visits will only be reported if there does not appear to be a treatment-by-time interaction, either based on the interaction p-value or by a descriptive examination of the data, and the term for treatment-by-time interaction will not be included in the model.

Alternative approaches for the analysis of binary endpoints, such as random-effects models (including site as a random effect if doing so appreciably affects treatment effect estimates), chi squares tests of association or Fisher's exact tests, may be considered.

13.1.4 Missing Observations

One of the assumptions of MMRM is that missing observations are missing at random (MAR), i.e., missingness is unrelated to the variable for which the observation is missing but can be related to another variable on which data have been collected. This assumption is not testable. However, given the short time frame of data collection for exploratory endpoints (60 minutes), it is unlikely that data will be missing not at random (MNAR). It is also unlikely that a substantial proportion (> 10%) of Study Participants will have missing observations. Therefore, the MAR assumption will be considered adequate to address any missing observations for variables analyzed using MMRM.

GEE assumes missing observations are missing completely at random (MCAR); i.e., missingness is independent of all other information whether it was collected or not. Again, due to the short time frame of data collection, this assumption will be considered adequate.

If > 10% of Study Participants have missing observations for a given endpoint, multiple imputation may be used for sensitivity analyses. Under an MNAR model, imputations will be based only on subjects randomized to placebo. The imputation method will be fully conditional specification (FCS) regression with 25 imputations. The imputer's model will include observed values at each time point included in the analysis, including baseline if applicable.

13.1.5 Multiplicity

There will be no adjustments for type 1 error inflation due to multiplicity.

14. SEQUENCE OF PLANNED ANALYSES

14.1 Final Analysis

The only planned analysis is the final analysis, which will occur after study-level EOS, all clinical data have been entered into the data capture system, AE and concomitant medication data have been coded, quality control checks have been completed, all data queries have been resolved, protocol deviations have been identified, and the database has been locked.

15. CHANGES FROM THE PROTOCOL

Confidential Page 24 of 33

| Protocol | Change |
|--|---|
| Primary endpoints: AEs recorded over 60 min post dose and at Day 7 | Incidence, seriousness, severity, and relatedness to study treatment of adverse events (AEs) recorded over 60 minutes post dose and at Day 7 |
| Change from Baseline in the VAS and the NRS-11 listed as an exploratory endpoint. AOM symptoms and Device Experience Questionnaire were included as "exploratory objectives" but were not stated as "exploratory endpoints." | Change from Baseline removed as an exploratory endpoint (same as PID). The following endpoints were added as exploratory endpoints: • Presence of AOM symptoms • Response on Device Experience Questionnaire – Subject • Response on Device Experience Questionnaire – Study Staff Administering Treatment |
| Data listings will be sorted by treatment, subject number, and time point unless otherwise noted. Site included as a fixed effect in mixed models. Only observed cases will be included in the PID computations. | Listingswill be ordered by unique subject identifier, parameter, date, data collection time if applicable, nominal study visit, and analysis visit window if applicable. Site included as a random effect if doing so appreciably affects treatment effect estimates. If > 10% of Study Participants have missing observations for a given endpoint, multiple |
| SPID will be analysed using a linear model analysis of variance (ANOVA) with fixed effects for treatment, site, and baseline pain score. Missing data will be handled using the Last Observation Carried Forward imputation method. | imputation may be used for sensitivity analyses. SPID will be analyzed using MMRM. Site will be included as a random effect if doing so appreciably affects treatment effect estimates. If > 10% of Study Participants have missing observations for a given endpoint, multiple imputation may be used for sensitivity analyses. |
| For ear pain: Hodges-Lehmann point estimate and 80% 2-sided CI for the median of treatment effect differences between active and placebo will be provided. Statistical comparisons of ear pain, as measured by the VAS and the NRS-11, | There is no separate analysis for "ear pain"; covered by analyses of VAS and NRS-11. |

Confidential Page 25 of 33

| 1 | |
|---|---|
| between the treatments at 60 min post dose | |
| will be performed using an ANOVA model. | |
| Ear pain responder analysis: | Based on \geq 25%, 50% and 75% reduction |
| | |
| Based on \geq 50 and 75% reduction | Response will be analyzed using general |
| | estimating equations (GEE). |
| CIs will be calculated using a fixed-effects | |
| model. | |
| PGIC and CGI-I will be analyzed using a | Site included as a random effect if doing so |
| mixed-effects model for repeated | appreciably affects treatment effect estimates. |
| measures with treatment group, visit, and site | |
| as factors and baseline score (PGIC and CGI- | Baseline NRS-11 will be used as a covariate. |
| I) as a covariate. | |
| Prior and concomitant medications will be | Summaries for prior medications will be |
| summarised using frequencies and | based on the Randomized Population. |
| percentages of subjects by treatment | Summaries for concomitant medications will |
| using the Safety Analysis Population. | be based on the Safety Population. |
| | |
| Only safety assessments with both predose | All safety data will be summarized. |
| and post-dose data will be analyzed. | - |
| For appearance of the TM, 80% CIs will be | Statistical inference for appearance of TM has |
| calculated for the incidence of shifts from | been removed. |
| Baseline (0-60 min), from normal to abnormal | |
| for the right ear and, separately, for the left | |
| ear. If significance is found using 80% CIs, | |
| 90% and 95% CIs will also be tested. | |
| Extent of exposure will be described by | Total exposure will be expressed as number |
| whether the subject took any study drug. | of sprays and will be summarized both per |
| | nostril and overall. |
| | Within-subject analyses will be done for PID |
| | and SPID. |
| | |

Confidential Page 26 of 33

REFERENCES

- 1. International Conference on Harmonisation of Technical Requirements for Registration of Pharmaceuticals for Human Use, ICH Harmonised Tripartite Guideline, Statistical Principles for Clinical Trials (E9), September 1998.
- 2. American Statistical Association (ASA). (2018) Ethical Guidelines for Statistical Practice. Prepared by the Committee on Professional Ethics, April 2018. http://www.amstat.org/ASA/Your-Career/Ethical-Guidelines-for-Statistical-Practice.aspx.
- 3. International Conference on Harmonisation of Technical Requirements for Registration of Pharmaceuticals for Human Use, ICH Harmonised Tripartite Guideline, Structure and Content of Clinical Study Reports (E3), November 1995.

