5.2 Statistical Considerations

The information in this section is a summary of the planned statistical analyses. Further details are provided in the Statistical Analysis Plan (SAP). The SAP will be developed based on the latest version of the clinical protocol and eCRFs, and will be finalised prior to database lock. No database may be locked, or analyses completed, until the SAP has been approved.

The SAP will provide a detailed description for the handling of missing data, patient eligibility criteria for the analysis, and statistical methodology for the data summary and analysis of safety and efficacy variables. This protocol describes key analyses undertaken by WCT in collaboration with Novus Therapeutics. If differences occur between analyses described in the SAP and the current protocol, those found in the SAP will supercede analyses outlined in the protocol.

All statistical reporting will be performed using the validated software SAS[®] for Windows version 9.3 or higher (SAS Institute, Inc., Cary, NC, USA), unless otherwise specified. Data collected from all randomised subjects will be presented in data listings. Both observed values and mean change from baseline values for each subject will be given where applicable. Data listings will be sorted by treatment, subject number, and time point unless otherwise noted.

Data for individual subjects will be listed. Continuous variables will be summarised using number of non missing observations, mean, standard deviation, median, minimum, and maximum observed values, and observed value ranges (where applicable). Categorical variables will be summarised using the frequency count and the percentage of subjects in each category.

Any deviations from the analyses described below will be included in the SAP, which will be included in the clinical study report.

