5.2.6 Efficacy Analyses

5.2.6.1 Exploratory Analysis

Pain Intensity Difference (PID) & Sum Pain Intensity Difference (SPID) will be calculated as follows:

• PID will be calculated as:

$$PID_t = PI_t - PI_{Baseline}$$

Where t is the post-dose assessment timepoint

Where baseline is the predose assessment timepoint

• SPID will be calculated as:

$$SPID_{ti-ti+n} = \sum_{ti}^{ti+n} (PID_i) * (t_{i+1} - t_i)$$

Where PID_i is the pain intensity difference score calculated at each post-dose timepoint

Where t_i is the scheduled assessment time

Analyses for Continuous Data

PID (change from Baseline) will be computed for each post-dose assessment timepoint (10, 20, 30, and 60 min). Data will be analysed using a longitudinal mixed model for repeated measures with fixed effects for treatment, time, treatment-by-time interaction, study site, and baseline pain score. Subject will be the random effect. Treatment differences from control (placebo) will be estimated from the Least Squares Means (LSM) from the analysis model along with 80% confidence intervals (CIs) and associated 2-sided p-values. If significance is found using 80% CIs, 90% and 95% CIs will also be tested. Only observed cases will be included in the PID computations. Graphical displays of the LSM change from Baseline will also be provided by treatment.

Descriptive summaries for each PID timepoint will be provided by treatment along with the model output for test differences in the LSM. PID analyses will be conducted for both NRS-11 and VAS pain scales.

SPID will be analysed using a linear model analysis of variance (ANOVA) with fixed effects for treatment, site, and baseline pain score. Treatment differences from control (placebo) are estimated using the LSM from the analysis model along with 80% CIs and associated 2-sided p-values. If significance is found using 80% CIs, 90% and 95% CIs will also be tested. SPID analyses will be conducted for both NRS-11 and VAS pain scales. Missing data will be handled using the Last Observation Carried Forward imputation method.

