8.5 Missing Data

Listings will present data as reported. Missing or partially missing dates that are required for date-dependent definitions (e.g., treatment-emergent AEs, concomitant medications) will be assumed to be the most conservative date possible. For example, an AE with a completely

Confidential Page 12 of 33

missing start date will be considered treatment-emergent. Missing observations will not be imputed for summaries. Handling of missing observations for statistical inference is described in Section 13.1.4.

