12.1 Efficacy Parameters

12.1.1 VAS and NRS-11

Ear pain will be measured by VAS and NRS-11. Scores will be collected for each ear at Baseline and 10, 20, 30, and 60 minutes post dose.

The VAS consists of a 100 mm line anchored by 2 extremes of pain, with the left anchor representing "no pain" and the right anchor representing "worse pain." Study Participants mark the line where their pain is best represented between the 2 anchors. The VAS score is the distance from the left anchor to the Study Participant's mark.

Confidential Page 18 of 33

NRS-11 pain scores range from 0 to 10, with 0 representing "no pain" and 10 representing the "worst pain possible." NRS-11 \geq 5 reflects moderate to severe pain and is an inclusion criterion.

Listings will show observed values and absolute changes from baseline for each ear separately, for the sum over both ears, and for the maximum score across both ears. For both VAS and NRS-11, decreasing change scores from baseline indicate improvement and this will be footnoted in TFLs.

Endpoints

The following endpoints will be calculated for both VAS and NRS-11, unless otherwise indicated, using (a) the sum of scores over both ears, and (b) the maximum score across both ears:

- PID_{t_i} where i = 1 to 4 and t_1 , t_2 , t_3 , $t_4 = 10$, 20, 30, and 60 minutes post dose, respectively, and PID_{t_i} = score at time t_i score at baseline (ie, change from baseline).
- SPID_t I defined as

$$SPID_{t_{-}I} = \sum_{i=1}^{I} PID_{t_{-}i} (t_i - t_{i-1})$$

where I = 1 to 4, t_0 is baseline, and t_1 , t_2 , t_3 , t_4 are time points 10, 20, 30, 60 minutes post dose, respectively. For example, SPID₂ is the sum of changes from baseline at 10 and 20 minutes post baseline weighted by time (in minutes) since the previous measurement.

- Percent change from baseline (per inclusion criteria, baseline VAS and NRS-11 are unlikely to be 0).
- Presence of any pain, defined as score > 0 at 10, 20, 30, and 60 minutes post dose.
- Improvement categorized as "worsening" (positive change score), "no change" (0 change score), "improvement" (negative change score) at 10, 20, 30, and 60 minutes post dose.

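### The SAP models cumulative SPID without a rule for a missing component score, so pain scores that were observed can drop out of the SPID model

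*SAP*

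**What the plan says.** Protocol Section 5.2.6.1 analyses SPID by ANOVA and gives a missing-data rule for it: "Missing data will be handled using the Last Observation Carried Forward imputation method". Protocol Section 5.2 lets the SAP override this, since where the two differ "those found in the SAP will supercede analyses outlined in the protocol". SAP Section 15 logs the change: "SPID will be analyzed using MMRM".

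SAP Section 12.1.1 defines SPID at 10, 20, 30 and 60 minutes as a cumulative sum of PIDs. In its own example, the second SPID "is the sum of changes from baseline at 10 and 20 minutes post baseline weighted by time (in minutes) since the previous measurement". PID and SPID each get their own MMRM.

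On missing data, SAP Section 8.5 says "Missing observations will not be imputed for summaries". For inference, SAP Section 13.1.4 makes one general statement: "the MAR assumption will be considered adequate to address any missing observations for variables analyzed using MMRM". It supports this with the short collection period and the expectation that "It is also unlikely that a substantial proportion (> 10%) of Study Participants will have missing observations". Above 10%, multiple imputation is an option for sensitivity analysis. No section says what SPID is when a component PID is missing.

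**The concern.** An MMRM on PID handles an isolated missing score well, because the participant's other scores stay in the model and inform the missing one. A cumulative sum lacks this property. Once one term is missing, that sum and all later sums are undefined, and the later scores reach the SPID model only through those sums. The model is then given less information than was collected.

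Three things are at stake. SPID loses precision for no reason. The SPID and PID results can rest on different participants. And because there is no rule, a programmer might sum whatever terms are available, which silently counts the missing interval as zero change. Two programmers following the same SAP could report different SPIDs.

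**Working it through.** The documents state no power, standard deviation, correlation or missingness rate for SPID, so there is no figure of theirs to reproduce. The inputs from the documents are 12 participants per arm (Protocol Section 5.2.1), the SPID formula (SAP Section 12.1.1) and the 10% threshold (SAP Section 13.1.4).

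**1. Weights.** The intervals before 10, 20, 30 and 60 minutes are 10, 10, 10 and 30 minutes, so SPID60 = 10·PID10 + 10·PID20 + 10·PID30 + 30·PID60. An illustrative profile of −1, −2, −3, −4 gives −10 − 20 − 30 − 120 = −180.

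**2. What one missing score removes, with the formula as written.**

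| Missing score | SPIDs undefined | Observed later scores unused | Their weight (of 60 min) |
|---|---|---|---|
| 10 min | 10, 20, 30, 60 | 3 | 10 + 10 + 30 = 50 |
| 20 min | 20, 30, 60 | 2 | 10 + 30 = 40 |
| 30 min | 30, 60 | 1 | 30 |
| 60 min | 60 | 0 | 0 |

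With a missing 10-minute score the participant contributes nothing to the SPID model. Monotone dropout behaves like the last row: no observed score is lost.

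**3. Does the fallback apply?** 10% of 24 is 2.4, so one or two affected participants do not trigger it. Three (3/24 = 12.5%) do, but the imputation is then optional and for sensitivity only. The SAP does not say whether pain scores or SPIDs would be imputed.

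**4. Precision (ignoring the small change in degrees of freedom).** For two participants without a 10-minute score, the standard error of the treatment difference grows by:
- one per arm: √(24/22) = 1.044, or 4.4%
- both in one arm: √[(1/10 + 1/12)/(1/12 + 1/12)] = √1.1 = 1.049, or 4.9%

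For one arm's mean SPID60, losing 1, 2 or 3 of 12 gives √(12/11) = 1.044, √(12/10) = 1.095 and √(12/9) = 1.155.

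The comparator is the 10, 10, 10, 30 contrast of PID MMRM means. Its precision was calculated with assumed known covariances (AR(1) or compound symmetry, correlation 0.3 to 0.9). With 1 to 3 of 12 lacking the 10-minute score, the contrast's standard error rises by only 0 to 1.0%. With 2 of 12 missing a single score:

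| Missing score | MMRM on SPID | PID contrast |
|---|---|---|
| 10 min | 9.5% | at most 0.6% |
| 20 min | 1.0 to 8.3% | at most 0.6% |
| 30 min | 0.5 to 7.0% | at most 0.6% |

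For a missing 60-minute score the two methods lose the same amount.

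**5. Bias.** One arm was simulated with 200,000 participants, PID means −1, −2, −3, −4, SD 2.5 and AR(1) correlation 0.7, all assumed. The true SPID60 is −180.

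| Mechanism | Missing | MMRM on SPID | PID contrast |
|---|---|---|---|
| 10 min, completely at random | 20% | 0.05 | 0.09 |
| 20 min, depends on PID10 | 28% | −0.11 | 0.12 |
| 30 min, depends on PID20 | 28% | −0.08 | 0.12 |
| 10 min, depends on later PID20 | 28% | −34.5 | 0.12 |
| 20 min, depends on later PID30 | 28% | −25.9 | 0.14 |

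The SPID model is essentially unbiased in the first three rows. It fails only when missingness depends on a later score that the sum has discarded. Those two rows assume far more missing data than the SAP expects, and they concern one arm's mean, not the treatment difference.

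**6. The unstated alternative.** Summing the available terms of the step 1 profile gives −170, −160 or −150 in place of −180 when the 10-, 20- or 30-minute score is missing.

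**The case against.** The strongest reply is that little turns on this. The primary endpoints are safety, SPID is one of many exploratory endpoints, collection lasts 60 minutes on site, little missing data is expected, and the PID MMRM already uses every observed score. The move away from LOCF is disclosed in SAP Section 15. All of this stands and limits the weight of the point. It does not supply the missing rule.

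A reader might go further in four ways that the documents do not support.
- **That the MAR statement is false for SPID.** SAP Section 13.1.4 calls MAR untestable and judges it adequate. The SPID model is unbiased when missingness depends on earlier pain. The fair criticism is that the general statement does not address scores discarded in forming the sum.
- **That dropping LOCF created the 10-minute problem.** At 10 minutes there is no earlier post-dose value to carry forward. Carrying baseline forward would set PID10 to zero, so restoring LOCF is not a clean remedy.
- **That a late 10-minute score is excluded.** The windows in SAP Section 8.7 are contiguous from 0 to 75 minutes, so a score at 15 to 24 minutes is assigned to minute 20. Minute 10 can still be left empty, but the documents do not suggest that this will be common.
- **That a missing 60-minute score does the most damage because it carries the largest weight.** That would require summing available terms, a rule the SAP never states. Under its formula, no observed score is lost in this case.

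**Conclusion.** The point holds as a gap in the SAP with a better method readily available. With the formula as written, an isolated missing score at 10, 20 or 30 minutes removes later observed scores from the SPID model while the PID model retains them. The expected cost is modest: about 4% on the confidence interval if 2 of 24, one per arm, lack a 10-minute score. That rate is assumed, as are the correlations, means and SD above. Material bias needs missingness tied to the dropped later scores, which is hard to picture in a supervised one-hour session.

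The SAP's interval weights also differ from the protocol's formula, and Section 15 does not log this. That is a separate documentation matter and adds nothing to this point.

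**What to change.** Replace the separate SPID MMRM with linear contrasts from the PID MMRM that includes treatment-by-time interaction:

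- For SPID60, apply weights 10, 10, 10, 30 to the time-specific LS-mean differences. Use the partial sums for earlier SPIDs: 10; then 10, 10; then 10, 10, 10.
- Obtain the within-group SPID means in the same way from the LS means of each arm.
- Use Kenward-Roger confidence intervals where the unstructured covariance is kept. Otherwise the contrast follows the SAP's existing rule for structured covariances.
- Do this for VAS and NRS-11, and for both the sum and the maximum across ears.
- State that a participant's SPID in tables and listings is missing when any component PID is missing, and is not summed over the available terms.
- Record the change in SAP Section 15.

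Because SPID is a linear combination of PIDs, the contrast targets the same quantity and uses every observed score. The cost is SAP wording and a set of contrast statements, with the SPID tables and figures repopulated from them. No data collection changes, and one model is removed.
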